5.3 Method for Assigning Subjects

Subjects will not be randomized for this study

5.4 Concomitant Therapy

Subjects will take their medications as normal

5.5 Blinding of Study

This study is open-label

6 Screening and Visits

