4.2 Primary Endpoint

The primary endpoint for the study is change in AHI, defined as the difference in AHI between the diagnostic study and PSG 2 with the Bongo. A reduction in AHI to less than 10 or an AHI reduction by at least 50% from the baseline is considered clinically significant.

5 Study Design and Procedural Detail

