5.1 Study Outline and Design

This study is a prospective, non-randomized, open label, single-center clinical study for the BONGO NASAL EPAP device for the treatment of obstructive sleep apnea.

Subjects will have the following study schedule:

1. Screening
2. In-lab PSG 1 with the Bongo
3. 2 week at home use of the Bongo
4. In-lab PSG 2 with the Bongo
5. Study termination visit (may be completed the morning following PSG 2)

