To record data during a PSG with the Bongo, a sampling tube connecting the nasal insert to the pressure transducer is used. Each nasal insert has a sampling port for connecting a sampling tube. The sample tubes and instructions for use will be supplied by InnoMed to the site for this purpose.

During PSG 1:

1. Subjects may sleep in the position that is the most comfortable for them.
2. All subjects will begin with the R1 valve in place.
3. Subjects will sleep with the R1 valve until the completion of one REM cycle. Calculate the AHI at this time.
 - a. If the AHI is below 10 (AHI < 10), maintain the R1 valve.
 - b. If the AHI equals or exceeds 10 (AHI ≥ 10), change to the R2 valve for the remainder of PSG 1.
4. Continue to calculate the running AHI of subjects that remained on the R1.
 - a. If the running AHI equals or exceeds 10 (AHI ≥ 10), change to the R2 valve for the remainder of PSG 1.

5. At the end of PSG 1 and prior to the subject leaving the facility:
 - a. Calculate and record the AHI for the overall time the R1 valve was used.
 - b. If applicable, also calculate and record the AHI for the overall time the R2 valve was used. (Note that the AHI for R1 and R2 should not be combined).

Prior to the subject leaving the facility, the research staff will need to score and assess whether the subject qualifies for the at home portion of the study. Score using the AASM 3% and/or arousal criteria.

1. Compare R1 AHI, as well as the R2 AHI (if applicable), to the subject's baseline AHI (from their diagnostic study).
2. If the subject while using the Bongo had an AHI reduction to less than 10 (AHI < 10) or an AHI reduction by at least 50% (AHI reduction $\geq 50\%$) compared to the baseline, then the subject qualifies for the at home portion of the study.
 - a. Send the subject home with either the R1 or R2 valve only, whichever valve the subject had the lowest AHI with.
3. If the subject did not have the AHI reductions described above with either valve, then that subject will be terminated from the remainder of the study.

Subjects that qualify for the at home portion of the study will continue using the Bongo at home for two weeks. Subjects will complete a daily use log while using the Bongo at home.

Enrollment will continue until such time a total of up to 10 subjects have completed all components of the study.

In preparation for the home use portion of the study, the site will:

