- Remove the sampling tubes from the Bongo and cover the Bongo sampling ports with caps provided by InnoMed prior to the subject going home
- Subjects will be provided with the instructions for use.
- Instruct the subject to call the site if any adverse events are experienced.

After two weeks (14 days) of at home use with the Bongo, the subjects will return with their Bongo unit and daily use log to the site for PSG 2. PSG 2 should be conducted no later than three days (14+3 days) after the end of the at home use portion of the study.

During PSG 2:

1. All subjects will use either the R1 or the R2 valve (the same device) that they have been using during the at home use period for the entirety of PSG 2.
2. Subjects may sleep in the position that is the most comfortable for them.
3. Calculate and record the AHI for the overall time.

Score using the AASM 3% and/or arousal criteria. PSG 2 studies to be scored no more than 3 days following the PSG 2.

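### The protocol does not say who scores PSG 2, or keep baseline AHI, PSG 1 AHI and valve from that scorer, although PSG 2 supplies the primary endpoint

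*Combined protocol and SAP*

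**What the plan says.** - **Blinding.** Section 5.5 consists of one statement: "This study is open-label". Section 5.1 describes the design in the same terms: "This study is a prospective, non-randomized, open label, single-center clinical study".
- **Endpoint.** Section 4.2: "The primary endpoint for the study is change in AHI, defined as the difference in AHI between the diagnostic study and PSG 2". The same section sets a benchmark: "A reduction in AHI to less than 10 or an AHI reduction by at least 50% from the baseline is considered clinically significant".
- **PSG 1 scoring.** Section 6.2 requires that, before the subject goes home, "the research staff will need to score and assess whether the subject qualifies for the at home portion of the study". The comparison is explicit: "Compare R1 AHI, as well as the R2 AHI (if applicable), to the subject's baseline AHI (from their diagnostic study"). The qualification thresholds are the same as the section 4.2 benchmark, and subjects who miss them leave the study.
- **PSG 2 scoring.** Section 6.2 repeats the 3% and/or arousal rule and sets a time limit: "PSG 2 studies to be scored no more than 3 days following the PSG 2". It names no scorer and says nothing about what the scorer may know.
- **Related text.** Section 13.1 limits data review to those who need it, as a confidentiality measure. Section 14.1 mentions a manual of operations, which is not among the documents and is not said to cover scoring. No central, independent or second reader appears anywhere.

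**The concern.** The study has no control arm and the subject cannot be blinded to the device. Masked reading of the endpoint recording is one of the few protections still available, and the plan does not use it.

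PSG 2 is read under a rule that admits arousal-based events, and these require judgement. Site staff will already have scored PSG 1 and set it against the diagnostic AHI. Nothing stops the same person, knowing those values and the valve, from scoring PSG 2. Knowledge of where a subject started, and of what was recorded two weeks before, can anchor borderline calls. The quantity at risk is the AHI change itself. The target is at most 10 completers (section 8.1) and reporting is descriptive (section 8), so there is little in the study against which a shift could be detected.

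The gap is also easy to narrow. PSG 1 has to be scored before discharge because it decides qualification and valve. PSG 2 decides nothing about the subject's further participation and has a three-day window.

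**Working it through.** The plan gives no figure on scorer agreement or bias, so there is none to reproduce. The check has two parts: what the text controls, and how much a leaning in scoring could matter under stated assumptions.

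**1. What the text controls**

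| Item | PSG 1 (section 6.2) | PSG 2 (section 6.2) |
|---|---|---|
| Scorer | Site research staff | Not stated |
| Rule | 3% and/or arousal | 3% and/or arousal |
| Timing | Before the subject leaves | Within 3 days |
| Compared with diagnostic AHI | Yes, to decide qualification | Yes, as the primary endpoint (section 4.2) |
| Baseline AHI, PSG 1 AHI or valve withheld | No provision | No provision |
| Score fixed before comparison | No provision | No provision |

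**2. Effect on the AHI change**

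Assume a fraction *u* of events is left out. The change then shifts by *u* × (PSG 2 AHI).

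- *u* = 10%: 0.10 × 10 = 1.0 and 0.10 × 13 = 1.3 events/h.
- *u* = 5%: 0.05 × 10 = 0.5 and 0.05 × 13 = 0.65 events/h.

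An overcount of the same size shifts the change equally the other way. The values of *u* and the AHI range 10 to 13 are assumptions.

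**3. Effect near the benchmark**

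For the AHI < 10 branch, take an AHI of 10.5 and an assumed 4, 6 or 8 h of sleep.

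- 4 h: 10.5 × 4 = 42 events. Below 10 means at most 39, so 3 fewer (7.1%).
- 6 h: 10.5 × 6 = 63 events. At most 59, so 4 fewer (6.3%).
- 8 h: 10.5 × 8 = 84 events. At most 79, so 5 fewer (6.0%).

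For the 50% branch, take baseline 24, where the mark is 24 × 0.5 = 12, and 93 events in 7 h (all assumed).

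- As scored: 93 / 7 = 13.3, a fall of 44.6%, which misses.
- *u* = 10%: 93 × 0.90 = 83.7 events; 83.7 / 7 = 12.0, a fall of 50.2%, which meets the mark.
- *u* = 5%: 93 × 0.95 = 88.4 events; 88.4 / 7 = 12.6, a fall of 47.4%, which still misses.

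Whether a subject crosses the mark therefore depends on the assumed figures.

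**4. What masking the baseline can hide**

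A subject meets the benchmark if AHI < 10 or AHI ≤ baseline / 2. The effective mark is the larger of 10 and baseline / 2.

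- Baseline 20 or less: baseline / 2 ≤ 10, so the mark is 10, which is printed in the protocol.
- Baseline 25: 12.5. Baseline 30: 15.

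Section 6.5 admits baselines from 5 to 30. Hiding the baseline leaves the mark visible over 20 − 5 = 15 of the 30 − 5 = 25 units of that range. This is a share of the range, not of subjects; the plan does not give the distribution of baselines.

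**The case against.** The strongest reply is that masking would achieve little here.

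- The benchmark of 10 is public and governs every baseline of 20 or less.
- Everyone who reaches PSG 2 is known to have met the criteria at PSG 1.
- The sampling-tube set-up may make the device recognisable in the trace.
- With one center, up to 10 completers and a three-day window, a lone scorer may recognise the subject despite a code.

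All of this stands and limits the benefit. It does not close the gap: the individual baseline and PSG 1 values can still be withheld, and those are what could anchor a continuous change score.

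Several stronger readings are tempting, but the documents do not support them.

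- **That section 5.5 makes scoring open.** It is silent on scoring. Open-label describes knowledge of treatment and does not rule out masked reading.
- **That PSG 1 is scored with the baseline in view.** Section 6.2 says to score and then compare; it does not say what the scorer sees while scoring.
- **That the bias must favour the device.** The direction is not shown. Section 6.5 words the diagnostic criterion as 3% hypopneas only, while PSG 2 also admits arousal-based events. Read literally, that difference works against the device, and masking PSG 2 alone does not address it.
- **That each reclassified subject moves a responder rate by 10 percentage points.** That is true of 1 in 10, but the plan specifies no responder-rate analysis and no study success threshold. Section 4.2 only labels the benchmark clinically significant.
- **That a second scorer is available on site.** Sections 6.2 and 12.1 mention research staff and a sleep technologist, but the number of qualified scorers is not given.

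Scorer assignment might be covered in the manual of operations. That cannot be checked, and the protocol does not refer to it for this purpose.

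**Conclusion.** The point holds as a gap in the plan for the primary endpoint. The PSG 2 scorer is not named, and nothing keeps baseline AHI, PSG 1 AHI or valve from that person, although the scoring rule involves judgement. The need-to-know wording in section 13.1 and the manual in section 14.1 do not supply the missing provision.

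The documents establish exposure to scorer bias. They do not show that it occurs, how large it is or which way it runs. The only size that can be given is conditional: 1.0 to 1.3 events/h on a PSG 2 AHI of 10 to 13 if 10% of events were missed, and half that at 5%. A reader might infer from the baseline-24 example that a modest leaning reliably turns a miss into a pass. It does so at 10% but not at 5%, so it should not be used as an estimate.

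This is an inexpensive improvement with partial benefit. It does not by itself invalidate the endpoint.

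**What to change.** Add to the PSG 2 part of section 6.2, with a cross-reference in section 5.5:

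> PSG 2 recordings are scored from a coded file without baseline AHI, PSG 1 AHI, valve or subject ID, and the PSG 2 AHI is locked on the CRF before the change from baseline is calculated. Where the site has another qualified scorer, PSG 2 is scored by someone who did not score that subject's PSG 1.

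The code should differ from the patient ID in section 13.1, because that ID already links all of a subject's case report forms.

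The study report should state that masking was partial, for these reasons:

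- the AHI < 10 mark is known and is the effective mark for any baseline of 20 or less;
- all PSG 2 subjects had qualified at PSG 1;
- the device trace may be recognisable;
- a single scorer at one center, working within three days, may recognise the subject.

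**Cost.** Coding about 10 files, and some scheduling where a second scorer exists. No extra visit or procedure is needed, and the three-day limit is unchanged. The coding and locking steps do not depend on a second scorer; the different-scorer step applies only where one is available.

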6.1 Screening/Baseline

Subjects will be first phone screened using existing patient rolls at each individual sleep center. Subjects who meet the initial qualifications will be asked to attend an in-clinic visit (Screening Visit).

During this Screening Visit the following will occur:

- Informed Consent Process
- Subjects will be asked to bring their CPAP/APAP machines and/or their data card for downloading and review. The following data from the past 30 days will be downloaded: pressure setting, average hours of use per night, % of time used, and residual AHI. If the subject has no data on their data card over this time period, and/or the subject has been diagnosed and is unable or willing to use CPAP, this will be noted on their record.
- Subjects will fit for the nasal inserts:
 - Subjects will select the size of the BONGO according to Bongo IFU
 - Subjects will be allowed a minimum of 10 minutes of acclimation with the valve R1; ensure that subject has some “supine” time during the acclimation period.
 - Subjects will be asked on a scale of 1-10 where their tolerability level of the device resides (<5, not qualified; ≥5, will qualify to move ahead).
- Once a subject is deemed eligible to participate, baseline measurements including BMI, vital signs, medications, and the above measures will be recorded.

6.2 PSG Studies

Two in-lab PSG studies will be performed while using the Bongo device. PSG 1 will be performed on a separate visit after the Screening Visit. PSG 2 will be performed after a two week (14 day) period of at home use with the Bongo.

Sites will follow the standard sleep protocol methods that include patient preparation procedures, the standard recording montage, the proper instrument calibration and bio-calibration procedures that must precede the initiation of the collection of the PSGs according to the American Academy of Sleep Medicine (AASM) Manual for Scoring Sleep and Associated Events (2007), a standard PSG montage, recording channel labels and the order to be used will be:

- left electrooculogram (E1/M2)
- right electrooculogram (E2/M1)
- submental electromyogram (chin1/chin2)
- submental electromyogram (chin2/chin3)
- electroencephalogram (C3/M2)
- electroencephalogram (O2/M1)
- electroencephalogram (F4/M1)
- electroencephalogram (C4/M1)
- electrocardiogram (ECG)

- thoracic inductance plethysmography (TEFFORT)
- abdominal inductance plethysmography (AEFFORT)
- nasal/oral nasal air pressure transducer (PFLOW),
- oxygen saturation (SaO₂)
- left anterior tibialis electromyogram (L LEG)
- right anterior tibialis electromyogram (R LEG)

Prior to each PSG, the site will screen the subject for acute alcohol intoxication by obtaining a breath alcohol test or equivalent. If testing shows any evidence of recent alcohol use, then the subject will be sent home after being counseled to refrain from alcohol use and return to the site within one week for the PSG. Subjects will be allowed no more than two attempts to participate if they are intoxicated upon arrival to the sleep clinic.

In addition, prior to each PSG, the site will call the subject to remind them of the upcoming PSG, they will be asked if they have any current cold or nasal condition which would prevent them from attending. At the time of the PSG, the research staff will assess the subject for nasal infection, nasal congestion, or nasal allergies that may impact the ability of the subject to breathe through the nose. If observation shows any evidence of nasal infection, nasal congestion, or nasal allergies, then the subject will be sent home and asked to return to the site after the symptoms have resolved.

[figure not shown]
A standard type pre (PM) sleep questionnaire will also be completed at a PSG visit. This questionnaire will assess the subjects day of test activity.

To record data during a PSG with the Bongo, a sampling tube connecting the nasal insert to the pressure transducer is used. Each nasal insert has a sampling port for connecting a sampling tube. The sample tubes and instructions for use will be supplied by InnoMed to the site for this purpose.

During PSG 1:

1. Subjects may sleep in the position that is the most comfortable for them.
2. All subjects will begin with the R1 valve in place.
3. Subjects will sleep with the R1 valve until the completion of one REM cycle. Calculate the AHI at this time.
 - a. If the AHI is below 10 (AHI < 10), maintain the R1 valve.
 - b. If the AHI equals or exceeds 10 (AHI ≥ 10), change to the R2 valve for the remainder of PSG 1.
4. Continue to calculate the running AHI of subjects that remained on the R1.
 - a. If the running AHI equals or exceeds 10 (AHI ≥ 10), change to the R2 valve for the remainder of PSG 1.

5. At the end of PSG 1 and prior to the subject leaving the facility:
 - a. Calculate and record the AHI for the overall time the R1 valve was used.
 - b. If applicable, also calculate and record the AHI for the overall time the R2 valve was used. (Note that the AHI for R1 and R2 should not be combined).

Prior to the subject leaving the facility, the research staff will need to score and assess whether the subject qualifies for the at home portion of the study. Score using the AASM 3% and/or arousal criteria.

1. Compare R1 AHI, as well as the R2 AHI (if applicable), to the subject's baseline AHI (from their diagnostic study).
2. If the subject while using the Bongo had an AHI reduction to less than 10 (AHI < 10) or an AHI reduction by at least 50% (AHI reduction $\geq 50\%$) compared to the baseline, then the subject qualifies for the at home portion of the study.
 - a. Send the subject home with either the R1 or R2 valve only, whichever valve the subject had the lowest AHI with.
3. If the subject did not have the AHI reductions described above with either valve, then that subject will be terminated from the remainder of the study.

Subjects that qualify for the at home portion of the study will continue using the Bongo at home for two weeks. Subjects will complete a daily use log while using the Bongo at home.

Enrollment will continue until such time a total of up to 10 subjects have completed all components of the study.

In preparation for the home use portion of the study, the site will:

- Remove the sampling tubes from the Bongo and cover the Bongo sampling ports with caps provided by InnoMed prior to the subject going home
- Subjects will be provided with the instructions for use.
- Instruct the subject to call the site if any adverse events are experienced.

After two weeks (14 days) of at home use with the Bongo, the subjects will return with their Bongo unit and daily use log to the site for PSG 2. PSG 2 should be conducted no later than three days (14+3 days) after the end of the at home use portion of the study.

During PSG 2:

1. All subjects will use either the R1 or the R2 valve (the same device) that they have been using during the at home use period for the entirety of PSG 2.
2. Subjects may sleep in the position that is the most comfortable for them.
3. Calculate and record the AHI for the overall time.

Score using the AASM 3% and/or arousal criteria. PSG 2 studies to be scored no more than 3 days following the PSG 2.

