Number of Subjects	Up to 10 subjects who complete
Diagnosis and Main Inclusion Criteria	
• ≥ 21 years of age• Diagnosis of mild to moderate obstructive sleep apnea via a PSG within the last 12 months
Study Product /Indication for Use	BONGO NASAL EPAP Device Intended for adult patients for the treatment of mild to moderate obstructive sleep apnea
Control/Comparator	None

3 Introduction

This document is a protocol for a human research study. This study is to be conducted according to US (21 CFR Part 812) and international standards of Good Clinical Practice (International Conference on Harmonization ICH-E6, ISO 14155 and other applicable government regulations, and Institutional research policies and procedures).

3.1 *Background*

Sleep is a necessary component of good health and comprises about one-third of a human life. The average person sleeps about 3000 hours per year; thus, the importance of sleep should not be underestimated. Adequate quantity and quality of sleep is essential to most psychological and physiological processes. Obstructive sleep apnea (OSA) is a common and serious condition that impairs sleep and can compromise an individual's health.

OSA can be characterized by a periodic full closure or partial obstruction in the upper airway due to neurological and/or anatomical features factors including micro- and retrognathia and impaired neuromodulation to the upper airway. Risk factors also include obesity, male, or post-menopausal females, age, neck size, and upper airway malformations such as deviated septum (Epstein, et al., 2009; Kapur, 2010). The obstruction or upper airways resistance results in cyclical reductions in blood oxygen, increased work of breathing, and arousals (cortical and sympathetic) from sleep. These sequelae may in turn have short- or long-term results such as insulin resistance, type two diabetes, stroke, incident coronary heart disease in men, neurocognitive deficits, and hypertension. Along with damage to health, these conditions may and also have significant negative workplace and economic consequences (Gottlieb et al., 2010; Marin, et al., 2005; Redeker & McEnany, 2011; Redline et al., 2010; Rosekind, et al., 2010; Yaggi, 2005).

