8.1 Sample Size

Up to 20 subjects may be enrolled in the study with a targeted number up to 10 subjects who complete the study and are deemed evaluable. A study with 10 subjects was proposed and accepted by the FDA for the data required for inclusion within a pre-market notification (510k) submission for the Bongo.

9 Subject Compliance Monitoring

Compliance for subject participation will be assessed at each visit.

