9.1 Early Withdrawal of Subjects

Although early withdrawal of subjects is not anticipated, for subjects who withdraw prior to completion of their participation, data collected to date will be included. If the withdrawal is due to medical reasons, appropriate referral to their primary care physician will be done.

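### The PSG 2 primary endpoint exists only for subjects who already met the same AHI threshold at PSG 1, so the PSG 2 responder rate overstates response among all treated subjects

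*Combined protocol and SAP*

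**What the plan says.** Section 4.2 makes change in AHI the primary endpoint, "defined as the difference in AHI between the diagnostic study and PSG 2 with the Bongo". It counts an AHI below 10, or a reduction of at least 50% from baseline, as clinically significant.

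Section 6.2 uses the same two-part threshold at PSG 1 to decide who goes on to home use. For a subject who misses it on both valves, or on R1 if only R1 was used, "then that subject will be terminated from the remainder of the study". It then says: "Enrollment will continue until such time a total of up to 10 subjects have completed all components of the study". Sections 6.4 and 8.1 cap enrolment at 20.

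Section 8 plans descriptive statistics. It gives no analysis set, no denominator and no rule for subjects stopped at PSG 1. Section 8.1 speaks of a "targeted number up to 10 subjects who complete the study and are deemed evaluable" and does not define evaluable. Section 9.1 says that "for subjects who withdraw prior to completion of their participation, data collected to date will be included", and section 9.1.2 is similar. Both concern withdrawal, not termination by the protocol.

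Section 2 describes the device as "Intended for adult patients for the treatment of mild to moderate obstructive sleep apnea".

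**The concern.** Everyone who starts PSG 1 is treated with the device. Only those who meet the success threshold that night can contribute to the primary endpoint, and those who miss it are replaced. Everyone with a PSG 2 value has therefore already succeeded once by the criterion then used to judge PSG 2.

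The intended population is adults with mild to moderate OSA, not adults who have had one successful night on the device. The study has no control group and no hypothesis test, so its meaning depends on which subjects are described. If the 510(k) data give a PSG 2 result without a prespecified denominator and label, a result for first-night responders can be read as a result for all treated patients.

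**Working it through.** **Inputs from the documents**

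- Endpoint: diagnostic AHI against PSG 2 AHI (section 4.2).
- Threshold: AHI below 10 or a reduction of at least 50%, at PSG 2 (section 4.2) and at PSG 1 (section 6.2).
- Baseline AHI: 5 to 30 (section 6.5).
- Up to 10 completers from up to 20 enrolled (sections 6.4 and 8.1).
- Not given: PSG 1 pass fraction, night-to-night variability, device effect, alpha, power.

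**1. The plan's own figure.** Section 8.1 gives no calculation to reproduce. The only arithmetic link is 10 / (1 − 0.5) = 20: the cap leaves room for half of those enrolled not to complete. The plan does not state 50%.

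**2. Direction.** Let S1 and S2 mean meeting the threshold at PSG 1 and at PSG 2. If subjects stopped at PSG 1 count as non-responders, and there are no other losses,

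P(S1 and S2) = P(S1) × P(S2 | S1).

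The completer rate is P(S2 | S1). The all-treated rate is that rate times the PSG 1 pass fraction. It is lower whenever at least one subject fails PSG 1 and at least one completer responds.

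**3. Size allowed by the enrolment limits.** If 10 complete, between 10 and 20 subjects began PSG 1. Some of the 20 may stop earlier: section 6.1 has subjects rate on a 1–10 scale "where their tolerability level of the device resides", and a score below 5 disqualifies. Responders with exact (Clopper-Pearson) 95% CIs:

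| Completers responding | Of 10 completers | Of 12 starting PSG 1 | Of 15 | Of 20 |
|---|---|---|---|---|
| 10 | 100% (69.2–100) | 83% (51.6–97.9) | 67% (38.4–88.2) | 50% (27.2–72.8) |
| 9 | 90% (55.5–99.7) | 75% (42.8–94.5) | 60% (32.3–83.7) | 45% (23.1–68.5) |
| 8 | 80% (44.4–97.5) | 67% (34.9–90.1) | 53% (26.6–78.7) | 40% (19.1–63.9) |

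If all 20 begin PSG 1 and 10 complete, the all-treated rate cannot exceed 10/20 = 50%.

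**4. Simulation under assumed inputs** (1.5 million draws per cell). True AHI is uniform 2–35 or lognormal (median 15, log SD 0.5), and subjects are kept if observed baseline is 5–30. Full-night SD is 3, 5 or 7 events/h, with half the variance shared within a night. PSG 1 is two half-nights, with a switch to R2 if the first half gives AHI of 10 or more. The valves are assumed equal, and the gate is passed if either meets the threshold. Losses for other reasons are not modelled. In the tables, *all treated* means as if everyone had PSG 2, and *sustained* means meeting the threshold at both PSGs, out of all treated.

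PSG 2 responder rate:

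| Device effect | All treated | Completers | Sustained |
|---|---|---|---|
| 60% reduction in half of subjects | 47–56% | 63–83% | 35–49% |
| Variable (mean 40%, SD 25%, limited to −20% to 95%) | 53–62% | 64–79% | 39–54% |
| Uniform 40% | 51–62% | 58–71% | 35–50% |
| None | 20–29% | 41–64% | 14–16% |

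Across cells, the completer rate is 4 to 44 points above the all-treated rate, and the sustained rate is 5 to 17 points below it. Rates are not zero without an effect partly because a subject with baseline AHI from 5 to below 10 can meet the threshold with no change.

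Mean AHI change (events/h):

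| Device effect | Completers | All treated |
|---|---|---|
| 60% reduction in half of subjects | −7.1 to −8.4 | −4.7 to −5.2 |
| Variable | −7.3 to −8.4 | −6.2 to −6.9 |
| Uniform 40% | −5.8 to −7.0 | −6.3 to −7.0 |
| None | −0.7 to −2.6 | +0.4 to −0.5 |

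In the uniform case at SD 3, the completers' mean change is the smaller one: −6.3 against −7.0.

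**5. A different noise model** (true AHI uniform 3–40, lognormal night-to-night CV 20–40%, one valve) gives the same direction for responder rates. With no effect, 60–77% of PSG 1 passers respond at PSG 2, against 20–25% of all treated. With a 50% median reduction it is 81–91% against 62–68%.

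**The case against.** The named endpoint is the continuous change in AHI; a responder rate is only implied by the clinical-significance threshold. For mean change, overstatement is not assured, as the uniform-effect case shows. That stands and limits the claim about the mean.

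The overstatement is zero if nobody fails PSG 1, and its size rests on assumptions: the two noise models agree on direction, not amount. That also stands.

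Section 6.2 states the gate and the replacement openly, so it can be read as a disclosed run-in, and PSG 2 among PSG 1 responders is a valid conditional result. True, but no section limits the conclusion to that group. Section 8 promises descriptive statistics for sleep study data, which could include PSG 1, but gives no denominator.

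Sections 4.1 and 8.1 record FDA discussion of the design and endpoints and acceptance of 10 subjects. Neither says that a completer-only analysis was agreed.

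The sample is also narrowed by CPAP history, mouth-breathing, mask type and tolerability. Those restrictions do not select on the outcome; the PSG 1 gate does.

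Finally, the valve rule in the fix rests on equal valves and half-nights, and the last valve used at PSG 1 need not be the one taken home. This is why the lower-AHI valve is to be shown alongside.

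**Conclusion.** The concern holds. Followed as written, the plan yields a primary result only for subjects selected by prior success on the same criterion, and nothing in it brings the others in or restricts the conclusion.

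For the responder rate, the direction against the all-treated denominator follows from the identity once anyone fails PSG 1 and any completer responds. Within the enrolment limits, with 10 completing, the completer rate can be up to twice the all-treated rate (20/10 = 2), and that extreme needs all 20 to reach PSG 1.

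The gap of 4 to 44 points over the all-treated PSG 2 rate depends on the simulation assumptions. Mean change is overstated when response varies between subjects or night-to-night noise is large, but not necessarily when response is uniform.

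Because this concerns the primary endpoint of an uncontrolled study, it should be settled before the data are analysed.

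**What to change.** Change analysis and reporting only; the PSG 1 gate and termination rule stay as they are. In section 8:

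1. Define the analysis set as all subjects who begin PSG 1 on the device.
2. Report the numbers enrolled, tested at PSG 1, passing PSG 1 and completing PSG 2.
3. Report the proportion meeting the section 4.2 threshold at PSG 2 with all who began PSG 1 as denominator. Count PSG 1 failures and subjects without PSG 2 as non-responders, and give a Clopper-Pearson 95% CI. Call it sustained response, and say that it is conservative because it requires passing twice.
4. Report baseline-to-PSG 1 AHI change for every treated subject with a 95% CI. Section 6.2 says "Note that the AHI for R1 and R2 should not be combined", so prespecify the valve: use the one in place at the end of PSG 1, show the lower of R1 and R2 alongside, and give sleep time on each. In the simulation the lower-of-two rule overstated the change by 0.7 to 2.7 events/h, against 0.2 to 0.7 for the last valve.
5. Report PSG 2 AHI change with a 95% CI, labelled as applying to PSG 1 responders who completed, and limit the conclusion to them.
6. Do not merge PSG 2 values for passers with PSG 1 values for failures into one estimate of change; the failures' values are selected for being high.

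In section 8.1, define evaluable and state that it does not filter the analysis set.

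**Cost.** Plan wording and one valve rule, with no added subjects or visits. AHI per valve is already recorded at PSG 1; sleep time on each valve must be tabulated from the same recording. The headline responder rate will be less favourable (5 to 17 points below the all-treated PSG 2 rate in the assumed scenarios), and the PSG 1 change rests on part-night values in subjects who switched valve.
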